Phase 2: After the SRC has confirmed acceptable safety in the Phase 1, a Phase 2, randomized, placebo-controlled study phase will be initiated, wherein approximately 66 subjects referred for SBRT with early stage large and/or central localized NSCLC will be randomized in a 1:1 ratio to receive either GC4711 100 mg or placebo given IV over 15 minutes on each day that SBRT is given, beginning the day of the first fraction of SBRT and ending the last day of SBRT,. SBRT is administered within 180 minutes (3 hours) of the end of the GC4711 infusion. A minimum of 18 hours and a maximum of 96 hours are permitted between fractions. All fractions should be given within 10 calendar days (+3 days in the case of a holiday or technical issue).

All subjects will be evaluated for changes in the in-field tumor for 24 months following completion of SBRT. The primary endpoint will evaluate the percentage of patients with complete or partial in-field tumor response through 6 months following SBRT. In addition, as a secondary endpoint, the percent of subjects with overall responses (PR + CR) per RECIST 1.1 will be evaluated.

All subjects will be evaluated by changes in the diffusion capacity of lung for carbon monoxide (DLCO), as assessed by the RTOG grading scale monitored at 6 months and 12 months. The secondary endpoints will evaluate all lung function parameters. Pneumonitis will also be assessed both clinically and radiographically (CTCAE 5.0).

All subjects will be followed for 30 days post SBRT completion for treatment related adverse events, 90 days post SBRT completion for acute radiation toxicity and for 12 months post SBRT completion for late radiation toxicity, and will be followed for 24 months post SBRT completion for local and regional disease control (LC), Progression Free Survival (PFS), Overall Survival (OS) and Distant Metastases (DM) rate.

Detailed information on the Radiation Therapy Quality Assurance (RTQA) (Phase 1 only) and dose-volume exposure, concomitant medications and existing obstructive lung disease will be collected for pneumonitis-risk analyses.

Pharmacokinetic (PK) sampling and cardiac monitoring will be performed on each subject with two separate doses of GC4711 (or placebo) collecting blood samples pre-infusion post-infusion and 24 hours post-infusion (Phase 1 only) for each.

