 - Exceeding these dose tolerances by more than 5% constitutes a major protocol violation.

By protocol prescription, the RT regimen consists of a 5-fraction treatment with doses between 10-12 Gy per fraction (Bejzak 2015) or 3-fraction treatment with doses of 18-20 Gy per fraction to the FDG-PET+ areas delineated as gross tumor volume (GTV). This target volume can be translated into an iGTV by including correction for 4D movement, no clinical target margins (CTV) are used. An additional 0.5 cm in the axial plane and longitudinal plane (craniocaudal) will be added to the GTV to constitute the planning target volume (PTV), while iGTV is reconstructed a 0.3cm margin is accepted. Larger margins may be used in cases where greater motion of the hemidiaphragm is observed in simulation despite standard maneuvers to diminish motion. No (nodal) elective field is given.

For purposes of dose planning and calculation of monitor units for actual treatment, this protocol will require tissue density heterogeneity correction. Successful treatment planning will require accomplishment of all the following criteria:

- Maximum dose: The treatment plan should be created such that 100% (60Gy) corresponds to the maximum dose delivered to the patient. This point must exist within the PTV.
- Prescription isodose: The prescription isodose surface must be >60% and < 90% of the maximum dose (60 Gy) covering the PTV.
- Prescription Isodose Surface Coverage: The prescription isodose surface will be chosen such that 95% of the PTV is conformally covered by the prescription isodose surface (PTV

V95%RX=100%) and 99% of PTV receives a minimum of 90% of the prescription dose (PTV V90%RX>99%).

Fractions should be given within 180 minutes from the end of the GC4711/placebo infusion. A minimum of 18 and maximum of 72 hours is permitted between fractions. Additionally, in case of machine break-down a 96-hour window is allowed. All fractions must be given within a maximum of 10 calendar days (+3 days in the case of a holiday or technical issue).

If SBRT administration is interrupted on any given day due to a machine break-down or other unforeseen circumstances, the rest of the treatment or a new SBRT session must be given as soon as possible. Rescheduling and SBRT dosing will be determined by the patient's treating physician in accordance with standard of care and covered with extra GC4711/placebo dosing. In case of a 6th fraction and/or dose of GC4711/Placebo may be given.

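### The mandatory PTV coverage criterion contradicts its own notation, and the reference dose in the same list does not fit the stated regimens (low severity)

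*Combined protocol and SAP*

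**What the plan says.** Section 6.2 (Stereotactic Body Radiation Therapy) introduces its planning criteria as compulsory: "Successful treatment planning will require accomplishment of all the following criteria". Three bullets follow.

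- **Maximum dose.** The 100% level is set at 60 Gy and must lie inside the PTV.
- **Prescription isodose.** "The prescription isodose surface must be >60% and < 90% of the maximum dose (60 Gy) covering the PTV".
- **Coverage.** The isodose is to be chosen so that "95% of the PTV is conformally covered by the prescription isodose surface". The parenthesis that restates this rule, and the second coverage rule after it, run: "V95%RX=100%) and 99% of PTV receives a minimum of 90% of the prescription dose (PTV V90%RX>99" (followed by a percent sign).

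Sections 4.8 and 6.2 give the regimens as 5 fractions of 10–12 Gy or 3 fractions of 18–20 Gy. Section 4.5 allows up to 20 Phase 2 sites.

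**The concern.** Each coverage rule is stated twice, in words and in notation. For the second rule the two versions agree. For the first they do not, and nothing elsewhere in the protocol says which governs. This is an operative acceptance threshold applied to every plan, so one site can accept a plan that another would reject or log as a deviation. Target coverage concerns the treated field, and the Phase 2 primary endpoint is in-field response.

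The rule is also defined relative to the prescription isodose, and the two bullets above it fix that isodose at a level that does not fit most of the regimen range. Correcting the parenthesis alone would leave the coverage rule tied to an inconsistent reference dose.

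**Working it through.** The plan gives no figure to reproduce here: no sample size or interval width depends on this criterion. The check is a logical comparison plus simple arithmetic.

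**1. What the notation means.** Write V(x) for the percentage of the PTV receiving at least x% of the prescription dose. The second clause puts 99% of the PTV at no less than 90% of the dose, and writes it V90%RX>99%. So the figure after V is dose and the right-hand side is volume.

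**2. The first clause under that convention.**

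- Words: V(100) at least 95%, taking the stated 95% as a minimum.
- Notation: V(95) = 100%.

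**3. Does the opposite convention help?** Read as volume then dose, the first parenthesis says that 95% of the volume gets 100% of the dose, which matches its sentence. The second would then say that 90% of the volume gets more than 99% of the dose, which does not match. For example, 95% of the PTV at 102% of prescription and 5% at 80% meets that reading. It fails the second clause's words, because V(90) = 95%, below 99%. No single convention fits both clauses.

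**4. Do the two versions differ in practice?** The dose distributions below are illustrative assumptions, not figures from the protocol.

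| Plan (share of PTV at % of prescription) | V(100) | V(95) | V(90) | Words | Notation | Second clause |
|---|---|---|---|---|---|---|
| A: 95% at 102, 5% at 92 | 95% | 95% | 100% | pass | fail | pass |
| B: 90% at 102, 10% at 96 | 90% | 100% | 100% | fail | pass | pass |
| C: 96% at 102, 4% at 97 | 96% | 100% | 100% | pass | pass | pass |

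The 102% stands for any dose above prescription. An isodose below 90% of maximum requires a peak above 1/0.90 = 1.11 times prescription. Placing such a peak within the 102% portion leaves all three V values unchanged.

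Plans A and B show that neither rule implies the other. Plan C shows that some plans satisfy both.

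**5. Redundancy.** V(x) cannot rise as x rises, so V(95) = 100% forces V(90) = 100%. Taken literally, the notation leaves the second clause with nothing to do.

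**6. Reference dose.**

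- Isodose range: 0.60 × 60 = 36 Gy and 0.90 × 60 = 54 Gy, so above 36 and below 54 Gy.
- Five fractions: 5 × 10 = 50 Gy to 5 × 12 = 60 Gy. Only totals from 50 to below 54 Gy fall inside the range.
- Three fractions: 3 × 18 = 54 Gy to 3 × 20 = 60 Gy. No total falls inside the range, because 54 Gy is not below 54 Gy.

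This takes the regimen total as the dose on the prescription isodose. If it meant the maximum dose instead, only a 60 Gy total would match the first bullet. Neither reading fits the full stated range.

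**The case against.** The strongest reply is that this is a slip in a gloss. Both rules are complete in prose and work together as a pair, and the redundancy in step 5 suggests that V95%RX=100% was never meant as a rival rule. Many planners may simply follow the sentence. This stands as to cause and weight. It does not make the text consistent, because a site cannot tell from the protocol which half governs. The parenthesis also breaks across a page and subscripts may have been flattened when the text was read. That lowers certainty about the exact typography but would not swap the two numbers.

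A reader might infer three stronger things, and the documents support none of them.

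- **Bias in the primary comparison.** Phase 2 is randomized 1:1, and investigators and site staff other than pharmacists are blinded (Section 8.2). Differing readings should therefore add noise, not favour an arm. Nothing in the documents quantifies a link from coverage to RECIST response. The protocol already permits larger variation: two fractionation schemes, a range of doses per fraction and variable PTV margins.
- **Loss of normal-tissue protection.** Organ limits are set separately in Tables 2 and 3 and apply under either reading. The violation grading ("Exceeding these dose tolerances by more than 5% constitutes a major protocol violation") concerns those limits. No grade is attached to PTV coverage.
- **No Phase 2 dosimetry.** Section 4.1 does restrict one item: "Detailed information on the Radiation Therapy Quality Assurance (RTQA) (Phase 1 only"). The same sentence adds dose-volume exposure without that limit, and Section 3 lists dosimetry in the exploratory analyses for both phases. However, those data are collected for pneumonitis-risk analyses, so PTV coverage is not certain to be among them.

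**Conclusion.** The inconsistency is real and shown by the text alone: a mandatory criterion says one thing in words and another in notation, and the versions can disagree about the same plan in either direction. Its likely origin is a transposition. The expected consequence is uneven plan acceptance and deviation calls across up to 20 Phase 2 sites. The documents describe no Phase 2 quality-assurance step that would catch this. That adds some variability but gives no reason to expect a difference between arms, and organ limits are unaffected. Severity is low.

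The reference-dose conflict in the same list belongs with it: on the plain reading, the isodose range excludes every three-fraction total and all five-fraction totals from 54 Gy upward.

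The conclusion rests on reading the notation by the convention of its neighbouring clause and the 95% in the sentence as a minimum. How often real plans would fall on different sides of the two rules cannot be judged from the documents.

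**What to change.** In Section 6.2, reconcile the coverage sentence with its parenthesis so that one criterion, stated identically in words and notation, applies at all sites. In the same correction, reconcile the 60 Gy maximum and the isodose range with the regimen totals in Sections 4.8 and 6.2, and state which dose the regimen total refers to. Which criterion and which dose are intended is for the sponsor to settle.

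The coverage correction is one line. The reference dose needs a few more in the same list. With a notice to sites, that is the main cost; sample size, endpoints and planned analyses are unchanged.

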Individual risk of radiation-induced pneumonitis depends on the volume of lung treated and the radiation dose administered, as well as patient characteristics and other treatment modalities used (immunotherapy itself has around 10% pneumonitis risk on its own ([Mohamad 2018](#))). The risk of clinical pneumonitis requiring medical intervention has been reported to be 9% to 28% after lung SBRT ([Kang 2015, Palma 2013, Yamashita 2014, Timmerman 2018](#)). Many more patients show radiological changes, which can often disturb response evaluation, as well as show milder changes which itself can limit retreatments for metastatic disease in the same lung ([Larici 2011, Kang 2015](#)). Significant (\geq grade 3) rates of pneumonitis have been reported varying from >10% to 21% ([Timmerman 2006, Baumann 2009, Stephans 2018](#)). Chemotherapy or/and immunotherapy carry their own pneumonitis risk and cumulative pneumonitis risk together with SBRT is observed and feared ([Zhao 2016, Mohamad 2018, Palma 2013](#)).

With improved systemic treatment, lung cancer patients are also living long enough to manifest late pulmonary toxicity after RT ([Larici 2011](#)). Moreover, in patients with recurrent disease, re-challenging RT also becomes technically possible. Based on nonclinical data, fibrosis obtained following the first SBRT treatment can significantly limit future treatment options. Due to their close relation to major airways, esophagus and major vessels, central tumors have a higher complication risk from radiotherapy, and are in general treated with 5 or more fractions of SBRT ([Lo 2009](#)) allowing normal tissue in the field more time to repair ([Timmerman 2006](#)).

In this trial, we target larger and/or central tumors associated with a higher pneumonitis and local failure risk, as well as a more fragile patient population. A sequential SBRT regimen of 5 fractions or 3 fractions for larger peripheral lesions delivering dose up till biologically equivalent (total) dose (BED) of 100Gy aligns with the standard dose for larger and/or central lesions ([Bejzak 2015](#), [Timmerman JAMA 2010](#)). The practice is shifting toward 5 fractions specifically for central localizations; however, for larger peripheral lesions, a 3-fraction regimen is still accepted.

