5.1 Inclusion Criteria

Participants are eligible to be included in the study only if all the following criteria apply:

1. Male or female subjects at least 18 years of age.
2. Ability to understand and the willingness to sign a written informed consent.
3. Histological or biopsy proven NSCLC. For peripheral lesions, cytology and/or clear imaging-guided suspicion is accepted if histology cannot be obtained.
4. ECOG performance status of 0-3.
5. Lymph node negative (T1 to T3N0M0), centrally located (within 2cm in all directions around the proximal bronchial tree, including ultra-central tumors, abutting the bronchial tree or trachea) or large (>1-7cm) Non-Small Cell Lung Cancer (NSCLC) , judged acceptable for SBRT by the treating Investigator. Staged with FDG-PET/CT, brain CT or MRI with contrast and/or mediastinoscopy, measurable disease as defined by RECIST 1.1. (See Figure 2 below).
6. Adequate end-organ function, based on routine clinical and laboratory workup:
 - a. ANC >1,000 cells/ μ l, Platelets \geq 75,000 cells/ μ l, Hemoglobin \geq 8.0 g/dl
 - b. Serum creatinine \leq 2 mg/dL or calculated creatinine clearance \geq 30 ml/min
 - c. Total bilirubin \leq 1.5 x ULN (or direct bilirubin below the ULN), AST and ALT \leq 2.5 x ULN
 - d. International normalized ratio (INR) (or prothrombin time (PT)) and activated partial thromboplastin time (aPTT) \leq 1.5 x ULN unless participant is receiving anticoagulant therapy, if values are within the intended therapeutic range
7. Males and females of must agree to use effective contraception starting prior to the first day of treatment and continuing after the last dose of GC4711/Placebo for 30 days (females) and 90 days (males).

[figure not shown]

Figure 2 Anatomy of central and ultra-central lung tumors

Timmerman and colleagues defined central lung tumors as those located within 2 cm of the proximal bronchial tree (Timmerman 2006). Here defined ultra-central lung tumors as those abutting the proximal bronchial tree or trachea (Lo 2010, Chaudhuri 2015, Chang 2018).

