5.2 Exclusion Criteria

Participants are excluded from the study if any of the following criteria apply:

1. Subjects with confirmed nodal and/or distant disease (including brain), according to standard workup by local investigator.
2. Subjects with peripheral lesions of 1cm or smaller
3. Prior treatment with immunotherapy within 3 months prior to Day 1 dosing.
4. Prior intra-thoracic radiotherapy or surgery with substantial overlap to planned in former radiation fields as determined by the treating radiation oncologist.
5. Subjects not recovered/controlled from prior treatment-related (chemotherapy or targeted therapy) toxicities judged by treating physician.
6. Uncontrolled malignancy other than lung cancer that requires active treatment or is deemed by the treating physicians to be likely to affect the subject's survival duration.
7. History of allergic reactions attributed to compounds of similar chemical or biologic composition to GC4711.
8. Uncontrolled intercurrent illness including, but not limited to, active infection, symptomatic congestive heart failure, unstable angina pectoris, cardiac arrhythmia, or psychiatric illness/social situations that, in the opinion of the investigator, would limit compliance with study requirements.
9. Participation in other clinical trials actively testing new anti-cancer treatments unless previous written approval provided by the Sponsor.
10. Requirement for concurrent treatment with nitrates or other drugs that may, in the judgment of the treating investigator, create a risk for a precipitous decrease in blood pressure.

11. Female subjects who are pregnant or breastfeeding.
12. Any other conditions that, in the Investigator's opinion, might indicate the subject to be unsuitable for the study.

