6.2 Stereotactic Body Radiation Therapy (SBRT)

SBRT Dosage, Administration, and Schedule

Patients will be evaluated by the treating radiation oncologist at the local site. Based on location and size of the tumor, dose planning will be determined by clinical appropriateness that balances ablation of the lesion(s) while respecting normal tissue constraints including for ultra-central lesions the volume criterium of the contoured proximal bronchial tree less than 0.03cc =<52.5Gy (Bejzak 2019).

Table 2 Organ Constraints for a 3-Fraction SBRT Regimen

Serial Tissue	Volume (cc)	Volume Max (Gy)	Max Point Dose (Gy) ²	Endpoint (\geq Grade 3)
Esophagus ¹	<5	27.9	32.4	Esophagitis
Brachial Plexus	<3	22	26	Neuropathy
Heart/Pericardium	<15	24	30	Pericarditis
Great vessels	<10	39	45	Aneurysm
Trachea and Large Bronchus ¹	<5	39	43	Impairment of pulmonary toilet
Bronchus smaller airways	<0.5	25.8	30	Stenosis with atelectasis
Rib	<5	40	50	Pain or fracture
Lung (Right & Left)	1500 for males; 950 for females ³	10.8		Basic Lung Function
Lung (Right & Left)			V-11.4Gy<37%	Pneumonitis
Spinal cord	<0.35	15.9	22.5	Myelitis

Abbreviations:

1. Avoid circumferential irradiation

2. “point” defined as 0.035cc or less

3. or one-third of the “native” total organ volume (prior to any resection or volume reducing disease), whichever is greater:

- Exceeding these dose tolerances by more than 2.5% constitutes a minor protocol violation.

- Exceeding these dose tolerances by more than 5% constitutes a major protocol violation.

Table 3 Organ Constraints for a 5-Fraction SBRT Regimen

Serial Tissue	Volume (cc)	Volume Max (Gy)	Max Point Dose (Gy) ²	Endpoint (\geq Grade 3)
Esophagus ¹	<5	32.5	38	Esophagitis
Brachial Plexus	<3	27	32.5	Neuropathy
Heart/Pericardium	<15	32	38	Pericarditis
Great vessels	<10	47	53	Aneurysm
Trachea and Large Bronchus ¹	<5	45	50	Impairment of pulmonary toilet
Bronchus smaller airways	<0.5	32	40	Stenosis with atelectasis
Rib	<5	45	57	Pain or fracture
Lung (Right & Left)	1500 for males; 950 for females ³	12.5		Basic Lung Function
Lung (Right & Left)			V-13.5Gy<37%	Pneumonitis
Spinal cord	<0.35	22	28	Myelitis

Abbreviations:

1. Avoid circumferential irradiation
2. “point” defined as 0.035cc or less
3. or one-third of the “native” total organ volume (prior to any resection or volume reducing disease), whichever is greater:
 - Exceeding these dose tolerances by more than 2.5% constitutes a minor protocol violation.

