divided into two sections: the proximal trachea and the distal 2 cm of trachea. The proximal trachea will be contoured as one structure, and the distal 2 cm of trachea will be included in the structure identified as proximal bronchial tree. Differentiating these structures in this fashion will facilitate the eligibility requirement for excluding patients with tumors within 2 cm of the proximal bronchial tree (see below).

- **Proximal Trachea:** Contouring of the proximal trachea should begin at least 10 cm superior to the extent of the PTV or 5 cm superior to the carina (whichever is more superior) and continue inferiorly to the superior aspect of the proximal bronchial tree (see the diagram definitions below).
- **Proximal Bronchial Tree:** include the most inferior 2 cm of distal trachea and the proximal airways on both sides as indicated in the diagram in Figure 2. The following airways will be included according to standard anatomic relationships: the distal 2 cm of RTOG 0618 (Timmerman 2018) trachea, the carina, the right and left mainstem bronchi, the right and left upper lobe bronchi, the intermedius bronchus, the right middle lobe bronchus, the lingular bronchus, and the right and left lower lobe bronchi. Contouring of the lobar bronchi will end immediately at the site of a segmental bifurcation.
- **Whole Lung:** Planning CT need to cover both entire lung volumes. Both the right and left lungs should be contoured as one structure. Contouring should be carried out using pulmonary windows. All inflated and collapsed lung should be contoured; however, gross tumor (GTV) and trachea/ipsilateral bronchus as defined above should not be included in this structure.
- **Skin:** defined as the outer 0.5 cm of the body surface. As such it is a rind of uniform thickness (0.5 cm) which envelopes the entire body in the axial planes. The cranial and caudal surface of the superior and inferior limits of the planning CT should not be contoured as skin unless skin is present in these locations (e.g., the scalp on the top of the head).
- All relevant normal tissue structures (e.g. spinal cord, lungs, heart, esophagus, brachial plexus, trachea and proximal bronchial tree, skin, etc.) are required in both planning images, as well as dose-volume histogram, for further contouring help see RTOG contouring atlas (<https://www.rtog.org/CoreLab/ContouringAtlases/LungAtlas.aspx>).

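### Section 6.2 cites an exclusion of central tumours that reverses inclusion criterion 5, and its airway limit for ultra-central lesions is not reconciled with Tables 2 and 3

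*Combined protocol and SAP*

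**What the plan says.** **Eligibility.** Section 5.1, criterion 5, admits node-negative tumours that are "centrally located (within 2cm in all directions around the proximal bronchial tree, including ultra-central tumors, abutting the bronchial tree or trachea"), or that are large. The only exclusion in Section 5.2 based on size or site is "Subjects with peripheral lesions of 1cm or smaller". Section 2.1 states the aim: "In this trial, we target larger and/or central tumors". The title and Section 4.1 agree. Section 6.2 (SBRT), under the critical-organ limits, splits the trachea into two contoured structures and says that this serves an "eligibility requirement for excluding patients with tumors within 2 cm of the proximal bronchial tree". It then points the reader to text below.

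**Airway dose.** The opening paragraph of Section 6.2 (SBRT) lists among the normal-tissue constraints, for ultra-central lesions, "the volume criterium of the contoured proximal bronchial tree less than 0.03cc =<52.5Gy". It names no fraction number. Table 3 (5 fractions) gives trachea and large bronchus a maximum point dose of 50 Gy; Table 2 (3 fractions) gives 43 Gy. Both tables define a point as 0.035 cc or less. Neither mentions ultra-central lesions. Under each table, an excess of more than 2.5% is a minor violation, and the next tier reads: "Exceeding these dose tolerances by more than 5% constitutes a major protocol violation".

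**The concern.** The contouring instructions rest on an eligibility rule that is the opposite of the one in Section 5. A reader who takes them at face value would think that central tumours, one of the two groups the trial is designed to enrol, are to be turned away. Section 5.4 gives failure to meet inclusion or exclusion criteria as an example of a protocol violation for which study treatment may be stopped, so a wrong statement about eligibility should not stand.

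The dose limits raise a different question: by which figure is an ultra-central plan judged? A plan can comply with the figure written for such lesions and be logged as a violation of the table. Up to 20 Phase 2 sites would each settle this alone. Section 4.1 marks the collection of radiotherapy quality-assurance information as Phase 1 only, so different local readings might not come to light. What is at stake is consistent application of normal-tissue limits, a violation log that means the same thing at every site, and possibly some added variation in delivered dose and coverage, on which in-field response plausibly depends.

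**Working it through.** **A. Eligibility texts side by side**

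| Place | Tumours within 2 cm of the proximal bronchial tree |
|---|---|
| Title, Section 2.1, Section 4.1 | Target population |
| Section 5.1, criterion 5 (same in the Synopsis) | Included, with ultra-central tumours |
| Section 5.2, all 12 criteria | Not excluded |
| Section 6.2 (SBRT), contouring of trachea and bronchial tree | Said to be excluded by an eligibility requirement |

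The pointer to text below leads to no such requirement; what follows is anatomical contouring. The statement stands alone against every other place.

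**B. Airway limits**

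Inputs: 52.5 Gy to 0.03 cc (Section 6.2 text); 50 Gy (Table 3) and 43 Gy (Table 2) point dose, trachea and large bronchus; violation thresholds 2.5% and 5%. The volumes can be compared, because 0.03 cc falls within the tables' definition of a point.

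| | Table 3, 5 fractions | Table 2, 3 fractions |
|---|---|---|
| Cap | 50 Gy | 43 Gy |
| Minor violation above (cap × 1.025) | 51.25 Gy | 44.075 Gy |
| Major violation above (cap × 1.05) | 52.5 Gy | 45.15 Gy |
| Excess at 52.5 Gy | 52.5/50 − 1 = 5.0% | 52.5/43 − 1 = 22.1% |
| Status at 52.5 Gy | Minor, at the edge of major | Major |

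In 5 fractions, a point dose above 50 and up to 52.5 Gy meets the text and exceeds the table. From just above 51.25 Gy up to 52.5 Gy it is a minor violation.

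Structures: the contours are the proximal trachea and the proximal bronchial tree. The latter takes in the distal 2 cm of trachea, the carina, and the mainstem and lobar bronchi, so it overlaps the trachea and large bronchus row. The tables have a separate row for smaller airways (40 Gy in 5 fractions, 30 Gy in 3), and nothing says which contour each row governs.

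**C. The planning criteria in the same section**

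The plan's total of 50 to 60 Gy (Section 4.8) reproduces: 5 × 10 = 50 and 5 × 12 = 60 Gy; 3 × 18 = 54 and 3 × 20 = 60 Gy.

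Section 6.2 requires all planning criteria to be met together. One sets the maximum dose at 60 Gy. Another puts the prescription isodose below 90% of it, so the prescription is below 0.9 × 60 = 54 Gy. A third requires nearly the whole planning volume (99%) to get at least 90% of the prescription. The coverage floor is therefore below 0.9 × 54 = 48.6 Gy, which is under the 50 Gy cap of Table 3.

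Read literally, and taking prescription as fractions × dose per fraction, the isodose criterion leaves no room for 5-fraction prescriptions from 54 to 60 Gy (54/5 = 10.8 Gy per fraction and above) or for any 3-fraction prescription (54 to 60 Gy), although the same section permits both. This is a separate inconsistency, which the same edit should reconcile.

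**The case against.** **The eligibility clause is not a criterion.** It explains why structures are drawn. Appendix 2 refers the reader to Section 5 for eligibility, and everything there admits central tumours. This stands as far as harm goes: a site following Section 5 will enrol correctly. It does not make the clause right. A reader might infer that the clause removes half of the intended population. The documents give no split between central and large peripheral tumours, so no share can be stated.

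**The two limits are both ceilings.** A plan at or below the lower one meets both, and the 52.5 Gy line can be read as one more constraint on top of the tables. Also, 52.5 Gy is exactly 105% of 50 Gy, so a 5-fraction plan within it is never a major violation on that row. All of this stands. But on that reading the one limit written for ultra-central lesions adds nothing to the trachea and large bronchus row. If it is instead meant as an exception, the protocol does not say so and the violation rule still applies. It also concerns ultra-central lesions only; for other central tumours the tables apply without conflict.

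**The 22.1% excess over Table 2 is a weak headline.** Section 2.1 associates 3 fractions with larger peripheral lesions and says that central tumours generally receive 5 or more. That stands, although Section 6.2 does not bar 3 fractions for ultra-central tumours.

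**A reader might infer that the coverage rule forces airway dose above the Table 3 cap**, because the planning margin around an abutting tumour overlaps the airway and 90% of 5 × 11.5 or 5 × 12 Gy is 51.75 or 54.0 Gy. The documents do not support this. Those floors need prescriptions of 57.5 and 60 Gy, which the isodose criterion in the same list rules out (working, C). The inference also needs more airway overlap than the 1% coverage allowance absorbs, and no overlap is given.

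**Effect on the comparison.** Treatment is randomised and investigators are blinded, dose within the permitted range is left to the treating radiation oncologist, and Section 8.5 plans no ultra-central subgroup analysis. No direction or size of bias can be claimed.

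**Conclusion.** Two internal contradictions hold on the text. The eligibility statement in Section 6.2 is wrong as written: it reverses criterion 5 and matches no exclusion. The airway limits for ultra-central lesions are unreconciled. In 5 fractions the gap is 50 to 52.5 Gy (5.0%), and the part that counts as a minor violation runs from above 51.25 Gy to 52.5 Gy. The Table 2 gap (22.1%) matters only if an ultra-central tumour is treated in 3 fractions.

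The dose finding assumes that the contoured proximal bronchial tree falls under the trachea and large bronchus row, which the anatomy supports but the document does not state. It does not show that a compliant plan is impossible. No sample size, precision or error-rate figure is affected. The consequence is inconsistent application of a normal-tissue limit and of violation grading, with an effect on the primary endpoint that is plausible but unquantified. It should be corrected, at moderate priority.

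**What to change.** In one amendment to Section 6.2 (SBRT):

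- Delete the eligibility clause, or reword it so that the contours identify and classify central and ultra-central tumours in line with criterion 5.
- Reconcile the 52.5 Gy text with the airway rows of Tables 2 and 3. State which limit governs ultra-central plans in each regimen, or that the regimen is not used for them.
- State which contoured structure each airway row applies to, and grade violations against the governing limit only.
- Reconcile the 60 Gy maximum and the isodose criterion with the permitted 5- and 3-fraction dose ranges.

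The choice of limits and doses belongs to the sponsor's radiation oncologists; this review takes no view on it. The cost is wording only, with no new procedures, assessments or patients.
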